6.3 Power considerations

The treatment success rate for each dose level of silymarin (π_{420} , π_{700}) is to be compared to that of placebo (π_0), where the success is defined as the normalization of ALT (≤ 45 IU/L) or a 50% decline to less than 65 IU/L. The primary null hypothesis of interest is H_{o1} : $\pi_0 = \pi_{420} = \pi_{700}$.

In the absence of silymarin, it is anticipated that the background rate (π_0) of spontaneous ALT normalization during a 24-week period may be as high as 0.15 (π_0 = 0.15). A clinically significant success rate would be in the neighborhood 0.40. An approximate idea of the statistical power afforded by the study to test H₀₁ can be obtained by considering the idealized scenario in which toxicity is not a concern, stopping rules for toxicity are not used, and a chi-square test is used to test H₀₁. Assuming that there is no dose response relationship (i.e. $\pi_{420} = \pi_{700}$) and 40% success in each treatment arm with 153 patients (51 per arm) will provide 80% power to reject the null hypothesis at α =0.05 using a chi-square test. On the other hand, if there is a dose response relationship and it is assumed that the probabilities of success are 0.15, 0.30, and 0.50 respectively for placebo, 420mg and 700mg, then with 51 patients in each group, at α =0.05 will provide 94% power to reject the null hypothesis. For participants who drop out, the last observation carried forward method will be used to impute the final outcome so that the last

available ALT would be used to determine the treatment success. Therefore, no overrecruitment to account for loss to follow-up is necessary.

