3.5 Premature discontinuation

Treatment may be discontinued prematurely for the following reasons:

- 1. Participant requests termination of the study medication;
- 2. Participant is intolerant of the study medication despite predetermined dose reductions and side effect management strategies;
- 3. Safety concerns at the discretion of the investigator. These concerns will be documented in the source documents.

Participants who discontinue treatment prematurely for the above reasons will be encouraged to remain in the post-treatment follow-up period for an additional 12 weeks, unless they withdraw consent. For those discontinued prematurely, data and blood samples will be obtained as listed for the week 24 end-of-treatment visit.

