6.2 Efficacy analysis

To address the primary objective 2, for each arm of the study, an estimate of the response rate π will be tabulated along with a corresponding 95% confidence interval. Point and interval estimates of mean change in log₁₀ (ALT) (a normalizing transformation) will also be tabulated.

The primary null hypothesis, H_{o1} : $\pi_o = \pi_{420} = \pi_{700}$, will be tested against the general alternative hypothesis, H_{a1} that response differs in at least one treatment arm via a chi-square test for association with $\alpha = 0.05$. If H_{o1} is rejected, then pair wise comparisons of the arms will be examined using a sequentially rejective test procedure (Holm, 1979).

Computation of these results for the intent to treat (ITT) analysis will comprise the main results of this study. Similar results will also be examined for the compliant-per-protocol subgroup of participants, defined as patients taking at least 80% of the medication.

Secondary analyses of efficacy will include model-based analyses of the relationship between dose and change in $log_{10}(ALT)$. Appropriate statistical models will be used in which change in $log_{10}(ALT)$ is the dependent variable. Study personnel will also perform analyses designed to aid interpretation of the main results or designed to be exploratory for purposes of hypothesis generation. For example, study personnel will use logistic regression models to investigate the relationship of pharmacokinetic exposure to treatment response.

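### Carrying dropouts' last ALT forward can score an early reading as week-24 success, and it does not justify making no allowance for dropout

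*Protocol*

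**What the plan says.** Protocol section 2.3 places the primary efficacy endpoint at the end of the 24-week treatment period: ALT at or below 45 IU/L, or at least halved to under 65 IU/L. Section 4.3 schedules treatment visits, each with an ALT, at weeks 2, 4, 8, 12, 20 and 24. Section 6.2 makes the intent-to-treat result the main result and tests it across the three arms, the alternative being "that response differs in at least one treatment arm via a chi-square test for association".

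Section 6.3 gives two power statements: "40% success in each treatment arm with 153 patients (51 per arm) will provide 80% power", with placebo at 15%; and 94% power when the "probabilities of success are 0.15, 0.30, and 0.50 respectively for placebo, 420mg and 700mg". For dropouts it says that "the last observation carried forward method will be used to impute the final outcome", using the last ALT available, and concludes: "Therefore, no overrecruitment to account for loss to follow-up is necessary".

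On patients who stop drug early, section 3.5 says: "For those discontinued prematurely, data and blood samples will be obtained as listed for the week 24 end-of-treatment visit". It encourages them to stay for 12 weeks of post-treatment follow-up, which section 4.4 sets as visits at follow-up weeks 4 and 12. The protocol states no expected dropout rate.

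**The concern.** Two things are at stake.

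The first is what the primary endpoint measures. A patient who leaves after week 2 or 4 with one low ALT is counted as a success at the end of 24 weeks. The plan itself allows that "spontaneous ALT normalization during a 24-week period may be as high as 0.15" without drug, so a single low reading cannot be presumed to last. If leaving differs between arms in frequency, timing or reason, the recorded success rates are biased. Section 5.0 acknowledges a heavy capsule burden, so some dropout is foreseeable.

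The second is the inference about sample size. Imputation fills the cell but adds no information about week 24. Power is unaffected only if dropouts' carried values succeed as often as the rates assumed for their arm.

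Section 3.5 might have limited the problem by supplying a real week-24 ALT for patients who stop drug. It names the set of samples but not the time: they could be drawn at stopping or at week 24 from randomisation. If at stopping, the follow-up visits land on week 24 only for someone who stops at week 20 (20 + 4) or week 12 (12 + 12).

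**Working it through.** **Inputs.** All from section 6.3 unless marked: 51 per arm, α = 0.05, three-arm chi-square test (2 df, critical value 5.99), success rates 0.15/0.40/0.40 or 0.15/0.30/0.50. The dropout fraction d is not in the protocol and is assumed, equal in all arms, at 5%, 10% and 15%.

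**Step 1: reproduce the stated power.** The noncentrality is λ = Σ 51(pᵢ − p̄)² / [p̄(1 − p̄)].

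- 0.15/0.40/0.40: p̄ = 0.3167; the squared deviations sum to 0.04167; λ = 51 × 0.04167 / 0.2164 = 9.82; power 80.8%. Exact enumeration of the three binomials gives 84.8%.
- 0.15/0.30/0.50: p̄ = 0.3167; the squared deviations sum to 0.06167; λ = 51 × 0.06167 / 0.2164 = 14.53; power 93.7% (exact 94.9%).

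The stated 80% and 94% therefore hold when every patient has a week-24 outcome at the assumed rates.

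**Step 2: carried values succeed at the placebo rate (assumed).** Each arm's rate becomes p(1 − d) + 0.15d. For the first scenario this is 0.15 on placebo and 0.40 − 0.25d on each silymarin dose. At d = 10% the rates are 0.15/0.375/0.375, p̄ = 0.30, and λ = 51 × 0.03375 / 0.21 = 8.20.

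| Dropout | Active rate | Power, noncentral chi-square | Power, exact |
|---|---|---|---|
| 0% | 0.400 | 80.8% | 84.8% |
| 5% | 0.3875 | 77.0% | 81.1% |
| 10% | 0.375 | 72.9% | 76.8% |
| 15% | 0.3625 | 68.3% | 72.0% |

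Exact power is 80.2% at 6% dropout and 79.4% at 7%, so it crosses 80% between them. In the second scenario, exact power is 90% at 10% dropout and 82.5% at 20%.

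**Step 3: milder or no dilution.** If dropouts keep half the effect, first-scenario power (noncentral) is 79.0%, 77.0% and 75.0% at 5%, 10% and 15%. If they keep all of it (0.15 on placebo, 0.40 on active), the rates are unchanged and nothing is lost.

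**Step 4: error in the other direction (assumed).** Let true week-24 success be 15% in every arm, let 20% of each silymarin arm drop out, and let 40% of those carry a low ALT. The recorded active rate is 0.80 × 0.15 + 0.20 × 0.40 = 0.20. With placebo recorded at 0.15, λ = 51 × 0.001667 / 0.1497 = 0.57, and the test rejects 9.5% of the time (exact 9.2%) against a nominal 5%.

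**Step 5: missing counted as non-success.** Each rate becomes p(1 − d). First-scenario power is 77.6%, 74.2% and 70.6% at 5%, 10% and 15% dropout (exact 81.9%, 78.6%, 75.0%).

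**The case against.** The strongest reply is that the loss is conditional. Section 6.3 presents its calculation as approximate and idealised, its figures reproduce, and if carried values succeed at the assumed arm rates there is no loss at all. That stands. A reader might infer that the stated power is wrong, or that carrying forward must dilute the silymarin arms; the protocol supports neither. What fails is the step from the imputation rule to no allowance for dropout.

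A reader might also infer that power falls below 80% with almost any dropout, because the approximation starts at only 80.8%. Exact calculation leaves room for about 6% even under the placebo-rate assumption, and the dose-response scenario has more to spare.

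Nor does the text show that every early stopper is carried forward. Section 3.5 separates stopping drug from leaving the study, section 6.3 applies the rule to those who drop out, and stopping at week 12 or 20 can still yield a week-24 visit. The fair criticism of section 3.5 is that its timing is unstated.

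Finally, counting missing as failure is also a single imputation, is itself biased if dropout is unequal, and does not restore power. At 10% dropout, 59 per arm (177 in all) would be needed for 80% by the noncentral method. That is true. Its advantage is that nobody is scored a week-24 success without a week-24 measurement. The scheduled week-24 ALT matters more, because it reduces what must be imputed.

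Sensitivity analyses may sit in a statistical analysis plan that is not at hand, so their absence is not criticised.

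**Conclusion.** The concern holds in limited form. The protocol fixes a dropout rule that lets an ALT from week 2 onwards stand for the end of 24 weeks, and draws from it a sample-size conclusion that needs an assumption it neither states nor justifies.

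The size cannot be fixed without a dropout rate. With equal dropout of 5% to 15% and carried values at the placebo rate, the first scenario loses about 4 to 13 percentage points of power by either method; the second stays at about 90% (exact) at 10% dropout. With transient dips concentrated in the silymarin arms, the false-positive rate could instead rise to about 9%. The direction depends on who leaves and when.

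This should be fixed, since it concerns the primary endpoint and a week-24 sample not taken cannot be recovered later. It does not invalidate the design or the complete-data power.

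**What to change.** 1. In section 3.5, state that patients who stop drug but remain in the study give an ALT sample at week 24 from randomisation, in addition to any sample at the stop visit, and that the intent-to-treat analysis uses it.
2. In section 6.3, count a week-24 ALT that is still missing as non-success in the primary analysis, and keep last observation carried forward as a sensitivity analysis.
3. Delete the sentence concluding that no extra recruitment is needed. Restate power with N = 153 over a range of assumed dropout. With missing as failure in the 0.15/0.40/0.40 scenario this is about 78%, 74% and 71% at 5%, 10% and 15% (exact 82%, 79%, 75%).

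The cost is protocol wording, one extra blood draw for patients who stop early, and a slightly less favourable stated power. Sample size and treatment rules are unchanged.

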6.4 Pharmacokinetic data analysis

A limited sampling strategy has been devised based on empirical/noncompartmental and model-based approaches. This approach evaluates the family of single point and paired concentrations (observed and interpolated) in order to define the minimal sampling scheme to yield adequate prediction of drug exposure (plasma AUC). A regression-based approach will be utilized using various discrete concentration permutations as predictors and AUC as the response. Based on the availability of a suitable structural model, these results will be validated with a model-based approach based on D-optimal design theory once preliminary data from the Phase I study is available. All modeling and simulations will be performed using the NONMEM software (Version V, Level 1.1, Globomax LLC; Hanover, MD).

Population PK model parameters (fixed and random) will be estimated via nonlinear mixedeffects modeling using NONMEM. An appropriate compartmental model/structure model will be developed for silymarin isomers based on the PK data collected in this study. Data from the Phase I study may be added to improve model stability. The effects of clinical and demographic factors, including but not limited to weight, height, body surface area, body mass index, ALT, age, and gender on PK model parameters will be investigated using a backward elimination procedure in NONMEM.

Individual predicted PK parameter estimates based on the final model will be used to explore the relationship between various PK metrics and clinical outcomes. Using a logistic regression, the probability of positive (or negative) outcomes will be predicted based on various PK metric expressions (i.e. Cmax, AUC).

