2.3 Endpoints

Efficacy: The primary outcome variable (endpoint) for efficacy is whether or not serum ALT (mg/dl) is \leq 45 IU/L (approximate normal range) or achieves at least 50% decline to less than 65 IU/L (approximately 1.5 times the upper limit of normal) at the end of the 24-week treatment period. The relationship between dose and change in log₁₀(ALT) will also be investigated as a part of secondary analysis plans.

Safety: The primary outcome variable for safety is the occurrence of a dose-limiting toxicity during the 24-week treatment period. All adverse events (AE) will be categorized by severity.

Adherence: Will be measured using a summary of missed dose information obtained from patient diaries and dose counts and will be analyzed as both an outcome and as an explanatory variable in exploratory analyses of pharmacokinetic exposure and response.

Biomarkers: The following relationships will be explored: dose and change in biomarkers, changes in biomarkers and rate of treatment success, changes in biomarkers and rate of toxicity.

Rationale for using serum ALT and not liver biopsy as an endpoint:

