3.3 Entry Criteria

Inclusion Criteria

To be eligible for this trial, patients must meet the following inclusion criteria:

- Age at least 18 years at screening
- Serum HCV RNA above quantifiable level of detection by any assay after the end of previous therapy
- ALT > 65 IU/L (i.e., approximately 1.5 X upper limit of normal) obtained during the screening period
- Previous treatment with any interferon-based therapy without sustained virological response
- Negative urine pregnancy test (for women of childbearing potential) documented within the 24-hour period prior to the first dose of silymarin. Females of childbearing potential must be using two reliable forms of effective contraception during the study (while on drug and during follow-up)

Exclusion Criteria

Patients with any of the following will not be eligible for participation:

- Use of silymarin or other milk thistle preparations within 30 days prior to screening
- Use of other antioxidants such as vitamin E, vitamin C, glutathione, alpha-tocopherol, or non-prescribed complementary alternative medications (including dietary supplements, megadose vitamins, herbal preparations, and special teas) within 30 days prior to screening. A multivitamin at standard doses will be allowed.
- Use of silymarin or other antioxidants or non-prescribed complementary alternative medications (as above) during the screening period or patient unwilling to refrain from taking these medications through completion of the study.
- Any antiviral therapy within 6 months prior to screening visit
- Known allergy/sensitivity to milk thistle or its preparations
- Evidence of poorly-controlled diabetes (defined as HbA1c > 8% in patients with diabetes)
- Use of warfarin, metronidazole or acetaminophen (greater than two grams per day) within 30 days of screening
- Lactose intolerance defined as patient reported inability to tolerate milk products
- Previous liver biopsy that demonstrated presence of moderate to severe steatosis or evidence of steatohepatitis
- Positive test for anti-HIV or HBsAg within 5 years of screening
- Average alcohol consumption of more than one drink or equivalent (>12 grams) per day or more than two (2) drinks on any one day over the 30 days prior to screening. Patients who met either criterion more than 30 days ago must have consumed a monthly average of 12 grams or less per day of alcohol for at least six months prior to screening.

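### The exposure-response model in section 6.4 leaves out baseline ALT, so this exploratory estimate may be confounded if ALT and exposure are related

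*Protocol*

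**What the plan says.** Section 6.4 describes a two-stage analysis. First, a population PK model is built, and backward elimination is used to test the influence of patient characteristics "including but not limited to weight, height, body surface area, body mass index, ALT, age, and gender on PK model parameters". Second, "Individual predicted PK parameter estimates based on the final model will be used to explore the relationship between various PK metrics and clinical outcomes": in a logistic regression, "the probability of positive (or negative) outcomes will be predicted based on various PK metric expressions", with Cmax and AUC as the metrics. Section 6.2 announces the same analysis: "study personnel will use logistic regression models to investigate the relationship of pharmacokinetic exposure to treatment response". Neither section names baseline ALT as a covariate in the outcome model, and neither excludes it. Section 6.4 does not say whether the ALT tested on PK is a baseline or an on-treatment value.

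Treatment response (section 2.3) is ALT at or below 45 IU/L at the end of the 24 weeks, or a patient who "achieves at least 50% decline to less than 65 IU/L". Entry requires a screening ALT of at least 65 IU/L, with no upper limit (section 3.3). Section 2.3 also plans adherence as an explanatory variable in exploratory analyses of exposure and response. Section 6.2 labels analyses of this kind as aids to interpretation or as hypothesis-generating.

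**The concern.** Randomisation protects the comparison of doses. It does not protect the comparison of patients with high and low AUC on the same dose. If baseline ALT goes with exposure and also governs the chance of response, a model without it credits exposure with an effect that belongs to baseline ALT.

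The protocol itself makes both links possible. ALT is a candidate PK covariate, and the exposure metrics come from the final PK model, so they carry ALT by construction if it is retained. The dose-selection text in section 1.0 adds plausibility: silymarin is extensively conjugated in the gut and liver, and a small loss of conjugation would greatly change free concentrations. ALT is an imperfect marker of liver function, so this is plausibility and no more. On the other side, response is an ALT rule whose stringency changes with baseline.

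If higher ALT goes with higher exposure, a useful drug could look flat or harmful as exposure rises. The opposite link could create a false exposure-response. Linking outcome to PK is one of the five PK goals in section 4.3.1 (there worded as a possibility), and secondary objective 3 covers PK and pharmacodynamics.

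**Working it through.** The protocol gives no figure for this analysis, so there is nothing to reproduce. The check has three steps.

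**1. Does the response rule depend on baseline ALT?** For baseline B, success needs a final ALT at or below about T(B) = max(45, min(B/2, 65)). The required fall is 1 − T(B)/B.

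| Baseline ALT (IU/L) | T(B) | Required fall |
|---|---|---|
| 65 | 45 | 1 − 45/65 = 31% |
| 80 | 45 | 44% |
| 90 | 45 | 50% |
| 130 | 65 | 50% |
| 160 | 65 | 59% |
| 200 | 65 | 68% |
| 300 | 65 | 1 − 65/300 = 78% |

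It does. Within the eligible range the required fall runs from 31% upward without a limit set by the entry criteria.

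**2. How large could the bias be if baseline ALT were known without error?** From the protocol: 102 active patients (2 × 51), doses of 420 and 700 mg, entry ALT of at least 65, and the response rule above. Assumed, because the documents do not give them:
- Baseline ALT is lognormal with median 105 and log-SD 0.45, cut at 65.
- ln AUC = ln dose + θ·ln(B/105) + noise, with a CV of 50% (log-SD = √ln(1 + 0.5²) = 0.47).
- ln final ALT = ln B − r·(ln B − ln 65) − 0.1 + noise, with log-SD 0.40. Here r is the regression towards 65 IU/L.
- There is no exposure effect. Each setting has 1,000 trials, so the Monte Carlo SE at 5% is √(0.05 × 0.95/1000) = 0.7 percentage points.

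| r | θ | Correlation of ln AUC with ln ALT | PK-only: OR per doubling; rejection | With ln baseline ALT: OR; rejection |
|---|---|---|---|---|
| 0 | 0 | 0.00 | 1.01; 3.9% | 1.00; 3.7% |
| 0 | 0.25 | 0.17 | 0.82; 4.9% | 0.97; 4.0% |
| 0 | 0.5 | 0.32 | 0.74; 7.4% | 0.96; 3.5% |
| 0 | 1 | 0.55 | 0.62; 15.3% | 0.96; 3.6% |
| 0.3 | 0 | 0.00 | 0.98; 4.3% | 0.98; 4.6% |
| 0.3 | 0.25 | 0.17 | 0.93; 4.3% | 0.99; 4.9% |
| 0.3 | 0.5 | 0.32 | 0.86; 6.4% | 1.01; 4.5% |
| 0.3 | 1 | 0.56 | 0.79; 9.0% | 1.01; 4.1% |

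With an exposure CV of 80% and θ = 1 (correlation 0.44), PK-only rejection is 8.6% (r = 0) and 7.6% (r = 0.3). Success rates are about 7% (r = 0) and 12% to 13% (r = 0.3), that is 102 × 0.07 ≈ 7 and 102 × 0.125 ≈ 13 successes.

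**3. What remains when baseline ALT is measured with error?** Recorded ALT varies around a patient's true level, so adjustment cannot be complete. In a simulation again of 102 active patients with no drug effect and assumed inputs, a correlation of 0.3 to 0.5 gave a PK-only odds ratio per SD of exposure of 0.82 to 0.74, with rejection of 7% to 13%. With baseline ALT added, the odds ratio was 0.91 to 0.88 and rejection 4% to 8%. At zero correlation nothing was lost. With an assumed true effect and a correlation of 0.3, power rose from 48% to 67%. That gain depends on the effect assumed, so only its direction should be relied on.

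**The case against.** The strongest case against is that the text is merely silent. It does not say that PK metrics are the only predictors, section 6.2 speaks of models in the plural, and section 2.3 already plans adherence as an explanatory variable. The covariates of an exploratory model are commonly left to an analysis plan, which is not shown. Much of this stands: a reader might infer that the protocol commits to PK metrics alone, and it does not. What remains is that section 6.4 does name the method, the outcome and the predictors, and in the same section names a possible common cause. Adherence does not close the ALT path.

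Second, ALT is only to be investigated and may be eliminated. This also stands. A reader might infer that the estimate is confounded; the documents assert no link between ALT and PK, and without one there is no bias.

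Third, the size depends on who enters the model, which the protocol does not say. With placebo patients included at zero exposure, a PK-only model under similar assumptions rejected in 4% to 5.5% of trials, although the odds ratio stayed below 1 (0.87 to 0.78). So excess false positives are not assured, but the distortion of the estimate persists.

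Fourth, one might go further and require assigned dose as a covariate, or extend the adjustment to toxicity. Neither is supported. Exposure is described as dose-proportional, so dose is the randomised part of exposure, and conditioning on it leaves only the non-randomised part. In one run, adding dose to baseline ALT gave odds ratios of 0.91 to 0.80, against 0.93 to 0.82 without it: no bias was removed. It also lowered power. For toxicity no comparable confounding argument has been made, and the 5% to 10% rates in section 6.1 give only 102 × 0.05 ≈ 5 to 102 × 0.10 ≈ 10 events.

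**Conclusion.** The point holds as a minor improvement. The exposure-response estimate for treatment response may be confounded by baseline ALT if ALT and exposure are related. Under the assumed inputs the bias is nil without a relation, small for a weak one (rejection of 4.3% to 4.9% at a correlation of 0.17) and material only for a strong one (9.0% to 15.3% at about 0.55). The documents give no ALT distribution, ALT-PK slope or exposure variability, so the true size and direction are unknown. The simulations took the link as positive; a negative one would push the odds ratio above 1.

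Adjustment reduces the bias but need not remove it. A reader might infer that the main efficacy result is at risk, or that this regression will set a later dose. The documents support neither: the primary chi-square test compares randomised arms and is unaffected, and no section gives this exploratory analysis a decision role.

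**What to change.** In sections 6.2 and 6.4, state that the exposure-response logistic models for treatment response include baseline log10(ALT), taken as the mean of the screening and Day 0 values, as a covariate next to the PK metric.

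State also that the ALT covariate, in the PK model and in the outcome model, is the baseline value. On-treatment ALT can be changed by treatment and, at week 24, decides the outcome. Using it as a PK covariate would carry the outcome into the exposure estimate, and adjusting the outcome model for it would be wrong.

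The cost is a sentence or two. ALT is already measured at both visits (Tables 3 and 4), and in the simulations error rates were no worse with the covariate when ALT and exposure were unrelated. Further covariates should be added sparingly: at the anticipated background rate of 0.15, 102 active patients give only about 15 successes (102 × 0.15 = 15.3).
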